- r This visit is for platelet count assessment and can be conducted on-site or remotely. Lab visits will occur weekly from Week 25 to Week 53. The Investigator can request that the participant visits the clinic for additional platelet monitoring during unscheduled visits if needed. After the end of treatment (EOT) visit, weekly platelet count assessment is not required; however, it is up to the Investigator to decide whether to conduct weekly platelet assessments using unscheduled visits, if deemed necessary for participant safety.

Table 3 - Schedule of Assessments - Long-Term Extension

	On-treatment clinic visits				Early Termination/ Unscheduled Visit
	Week 53/Rollover to LTE ⁿ	Clinic Visits Every 28 Days for the first year of LTE then every 3 months thereafter	Last Day of Active Rilzabrutinib Treatment	End of Study (4 weeks post-last dose)	
Visit Windows	±7 days	±7 days	±7 days	±7 days	
AEs	X	X	X	X	X
Concomitant Medications ^a	X	X	X	X	X
Weight (kg)	X	X	X	X	X
Physical Exam ^b	X	X	X	X	X ^m
ECG (12-lead, single)	X			X	X ^m
Vital Signs	X	X	X	X	X
Urinalysis ^c	X	X	X	X	X
Pregnancy test ^d	X	X	X	X	X
Serum Chemistry ^e	X	X	X	X	X
Hematology, differential, reticulocytes ^f	X	X	X	X	X
T/B/NK counts ^{g, k}	X	X		X	
PT/INR aPTT ^h	X	X	X	X	
TPO levels ^k	X	X	X	X	
Hemolysis panel ^{i, k}				X	
Immunoglobulin Levels ^k				X	
(Optional) sample for vaccine-specific IgG ^{k, l}	←=====→				X
QOL Questionnaires ^j	X	X	X	X	X
IBLS	X	X	X	X	X
Rilzabrutinib dispensed	X	X			
Patient Medication Diary	X	X			X ^m
SARS-CoV-2 test (see Appendix 10 for country-specific requirements)	X				X ^m

AE = adverse event; aPTT = activated partial thromboplastin time; CS = corticosteroids; ECG = electrocardiogram; EQ-5D-5L = EuroQOL-5 Dimension 5 Level; IBLS = ITP Bleeding Scale; IgG = immunoglobulin G; INR = international normalized level; ITP = Immune thrombocytopenia; ITP-PAQ = ITP-Patient Assessment Questionnaire; ITP-KIT = Kids' ITP Tools; PGIS = Patient Global Impression of Severity PGIS-Fatigue = Patient Global Impression of [Fatigue] Severity; QOL = Quality of Life; SD = study day; T/B/NK = T-lymphocytes/B-lymphocytes/natural killers; PGIC = Patient Global Impression of Change; PT = prothrombin time; TPO = Thrombopoietin; TPO- RA = thrombopoietin receptor agonist

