- a Reductions in the doses or withdrawal of concomitant ITP medications will be permitted if the participant achieves platelet count of ≥50,000/μL in three scheduled visits (over 12 weeks). Retreatment with the same medication(s) and doses of ITP concomitant medication(s) used at baseline (an oral CS and/or a TPO-RA), changing the dose or initiation of new ITP medications (an oral CS and/or a TPO-RA) will also be allowed. Tapering of concomitant CS and/or TPO-RA should be performed in accordance with the schedule in Section [6.6.2](#).

- b* Full physical exam at End of Study, abbreviated physical exam at all other visits. See [Appendix 10.6](#) for Italy-specific requirements.
- c* Urinalysis: pH, specific gravity, protein, glucose, ketones, bilirubin, blood, nitrites, urobilinogen, and leukocytes.
- d* Urine pregnancy test for women of childbearing potential only.
- e* Serum chemistry will include the following: aspartate aminotransferase (AST); alanine aminotransferase (ALT); total, direct, and indirect bilirubin levels; alkaline phosphatase (ALP); albumin; creatinine; urea; total protein; sodium; chloride; calcium; phosphate; potassium; and glucose (random).
- f* Hematology will include the following: hemoglobin, hematocrit, erythrocyte count (red blood cell [RBC] count), thrombocyte count (platelets), mean platelet volume, leukocyte count (white blood cell [WBC] count) with differential in absolute counts (including neutrophils, eosinophils, basophils, lymphocytes, and monocytes). Local laboratories will be used for platelet analysis required at ALL visits (ie, Clinic Visits and Unscheduled Lab Visits in between Clinic Visits). The central laboratory will to be used for the analyses required at Clinic Visits including hematology, differential, and reticulocytes. The results of hematology, differential and reticulocytes obtained at local laboratories will be used only if the central lab results of Clinic Visits are missing due to any reason. Central platelet counts assessed at Clinic Visits will be used if local platelet results are missing for any reason. After the end of treatment (EOT) visit, weekly platelet count assessment is not required; however, it is up to the Investigator to decide whether to conduct weekly platelet assessments using unscheduled visits, if deemed necessary for participant safety.

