3.2.3. Other Secondary Endpoints

3.2.3.1. Efficacy Endpoint

- Stability of response defined as the proportion of participants able to achieve stable platelet response, which is defined as no 2 scheduled visits, at least 4 weeks apart, with a platelet count less than 50,000/ μ L, without an intervening visit with a platelet count $\geq 50,000/\mu$ L, within a period of 24 weeks following initial achievement of the platelet response (initial platelet response defined as platelet count $\geq 50,000/\mu$ L within 12 weeks of initiation of treatment with rilzabrutinib during the study).

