### 3.3.2 Supportive secondary endpoint(s)

#### 3.3.2.1 *Other secondary endpoint – Stability of platelet response*

To qualify for a stable platelet responder (see endpoint definition in [Section 1.2.2.3.1](#)), a participant must have met ALL of the following criteria:

- Achieving initial platelet response, ie, platelet count  $\geq 50,000/\mu\text{L}$  within 12 weeks of initiation of rilzabrutinib [during double-blind period (protocol visit Week 2 to Week 13) for participants randomized to rilzabrutinib group, or during open-label period (protocol visit Week 26 to Week 37) for participants randomized to placebo group], and
- Following the initial platelet response, achieving platelet count  $\geq 50,000/\mu\text{L}$  for a period of 24 weeks, where
- There would be no 2 scheduled visits, at least 4 weeks apart, with a platelet count less than  $50,000/\mu\text{L}$ , without an intervening visit of platelet count  $\geq 50,000/\mu\text{L}$ . In other words, a participant would not be qualified for a stable responder if the participant has consecutive platelet counts  $< 50,000/\mu\text{L}$  for 4 weeks or longer (ie, from the first to the last occurrence of  $< 50,000/\mu\text{L}$  without any intervening visit of platelet count  $\geq 50,000/\mu\text{L}$ ) during this 24 weeks period after the initial response has been achieved. The participant's platelet counts within 4 weeks of rescue regimen will be considered as no response.
- Missing platelet count will be considered as no response.

The proportion of stable response will be calculated along with its 95% confidence interval (via normal approximation) in the open-label population ([Section 2](#)) as well as by randomized treatment group at the beginning of double-blind treatment, respectively.

For participants who are identified as a stable platelet responder, the duration of response will be descriptively summarized in the rilzabrutinib safety population ([Section 2](#)) as well as by randomized treatment group at the beginning of double-blind treatment, respectively. The duration of stable platelet response defined above is from the start date of stable platelet response up to

- The date of the first occurrence of 2 or more consecutive platelet counts  $< 50,000/\mu\text{L}$  for 4 weeks or longer (ie, when the stable response is lost), or
- 12 months after entering LTE,

whichever earlier.

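### Duration of stable response is summarized without censoring and capped 24 weeks apart in the two randomized groups, and the 24-week stability window is not defined past Week 53

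*SAP*

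**What the plan says.** The protocol (Section 3.2.3.1) defines stability as the absence of a sustained drop below 50,000/µL "within a period of 24 weeks following initial achievement of the platelet response", where the initial response must come within 12 weeks of starting rilzabrutinib. SAP Section 3.3.2.1 turns this into visit windows. The initial response is sought "during double-blind period (protocol visit Week 2 to Week 13) for participants randomized to rilzabrutinib group" and "during open-label period (protocol visit Week 26 to Week 37) for participants randomized to placebo group".

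The failure rule is "There would be no 2 scheduled visits, at least 4 weeks apart, with a platelet count less than" 50,000/µL and no intervening count at or above it. It applies "during this 24 weeks period after the initial response has been achieved". The section adds: "Missing platelet count will be considered as no response".

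The proportion is reported with a 95% CI in the open-label population and by randomized group. For stable responders, duration of response is summarized descriptively in the rilzabrutinib safety population and by randomized group. It ends at the earlier of loss of response and 12 months after entering the LTE.

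Weekly platelet counts stop at Week 53 (Protocol Table 2, footnote r). The LTE schedule is "Clinic Visits Every 28 Days for the first year of LTE then every 3 months thereafter" (Protocol Table 3). In the LTE, footnote a to Table 3 states that "changing the dose or initiation of new ITP medications (an oral CS and/or a TPO-RA) will also be allowed".

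**The concern.** Duration of response is a time-to-event quantity. Many participants will reach the cut-off still responding, or will leave the study without having lost response. A descriptive mean or median treats the cut-off as the end of response and gives no instruction for those who leave. Placebo-randomized participants start rilzabrutinib 24 nominal weeks later but share the same calendar cap, so their durations are cut shorter whatever the drug does. A reader who sees the two randomized groups side by side could take the difference for a treatment-history effect.

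The stability proportion has a related gap. The 24-week window of a late placebo-origin responder runs beyond the weekly schedule, and the SAP is silent on how those weeks are filled. This matters because missing counts are scored as no response.

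**Working it through.** **Inputs.** Nominal week n falls on Day 1 + 7(n − 1) (SAP Table 12). Hence Week 25 = Day 169, Week 37 = Day 253 and Week 53 = Day 365, which reproduces the plan's 28-week open-label period: (365 − 169)/7 = 28. LTE Month 1 = Day 393 = Week 57. LTE Month 2 = Day 421 = Week 61. LTE Month 12 = Day 701 = Week (701 − 1)/7 + 1 = 101.

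**Duration cap**, taking the initial response as the start date and LTE Month 12 as the cap:
- Rilzabrutinib-randomized, first response at Weeks 2 to 13: 101 − 13 = 88 to 101 − 2 = 99 weeks.
- Placebo-randomized, first response at Weeks 26 to 37: 101 − 37 = 64 to 101 − 26 = 75 weeks.
- Gap: 99 − 75 = 88 − 64 = 24 weeks.

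Day 701 is 336 days after Day 365, that is, twelve 28-day months. Reading the cap as 12 calendar months adds the same amount to both groups and leaves the gap at 24 weeks.

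**What the gap can do to a mean.** The documents give no loss rate, so this is an illustration. Assume an exponential time to loss after the first 24 weeks, with the same median m in both groups and λ = ln 2/m. With mid-range caps, the remaining observable time T is 93.5 − 24 = 69.5 weeks (rilzabrutinib-randomized) and 69.5 − 24 = 45.5 weeks (placebo-randomized). The capped mean beyond 24 weeks is (1 − e^(−λT))/λ, and the share still responding at the cap is e^(−λT).

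| Assumed m | Capped mean, rilzabrutinib / placebo | Difference | Still responding at cap |
|---|---|---|---|
| 30 weeks | 34.6 / 28.2 | 6.4 weeks | 20% / 35% |
| 60 weeks | 47.8 / 35.4 | 12.4 weeks | 45% / 59% |
| 120 weeks | 57.2 / 40.0 | 17.2 weeks | 67% / 77% |

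Identical loss rates therefore give apparently different durations.

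**Stability window.** Window end = first-response week + 24.
- Rilzabrutinib-randomized: Weeks 26 to 37, always on the weekly schedule.
- Placebo-randomized: Weeks 50 to 61. First responses at Weeks 26 to 29 (4 of 12 visits) finish by Week 53. Weeks 30 to 37 (8 of 12) overrun by 1 to 8 weeks.

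Take a placebo-origin participant whose observed counts are all at or above 50,000/µL:
- **Enters the LTE with high counts at Week 57, and at Week 61 where needed:** passes for every first-response week.
- **No LTE data, every week after 53 filled as missing:** passes for first response at Weeks 30 to 33, where the missing run spans at most 3 weeks. Fails automatically at Weeks 34 to 37, where it spans 4 to 7 weeks.
- **No LTE data, only SAP Table 12 visits filled as missing:** fails automatically only at Week 37, where Days 393 and 421 are both missing and 28 days apart.
- **Weeks without a scheduled visit not scored:** nobody fails for them, but a participant who does not enter the LTE may be judged on as few as 53 − 37 = 16 weeks.

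The same data can therefore give different classifications, and the SAP does not choose. Section 3.2 bases efficacy on each on-treatment period unless otherwise specified, and Table 10 limits the open-label step to open-label efficacy. The amendment 03 rationale for this endpoint, by contrast, names the LTE as a period of evaluation.

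**The case against.** A reader might infer that placebo-origin participants are systematically failed for weeks that were never scheduled. The documents do not support that. The failure rule refers to scheduled visits, and SAP Table 12 has no visit at Weeks 54 to 56 or 58. LTE entrants have counts at Weeks 57 and 61. The duration definition already runs into the LTE, so LTE data are evidently expected. Automatic failure needs one particular reading, a late first response and no LTE entry. LTE entry requires response at half or more of the visits in the last 8 open-label weeks, by a looser threshold and without rescue (Protocol Section 4), so most stable responders would qualify.

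A reader might also infer that the rule does not measure stability. Four weekly lows span only 21 days, so a repeated pattern of four lows and one high passes with 20 of 24 counts below 50,000/µL. That is an extreme. If half of counts are low, simulation gives a pass probability of 70% with independent weeks, but 29% and 20% at assumed week-to-week correlations of 0.5 and 0.7. The rule is the protocol's own (Section 3.2.3.1) and the SAP follows it. A stricter fraction would be a different endpoint, not a correction.

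The objective concerns rilzabrutinib, with no stated comparison against placebo, and no between-group test is planned. This limits the consequence. It does not answer the duration point, because the SAP reports duration by randomized group and leaves some participants without an end date.

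Censoring has its own weakness: leaving at Week 53 depends on response, and the primary analysis treats an increase in concomitant ITP medication as non-response (Protocol Section 10.3.9). Censoring at either is informative, so a sensitivity analysis is needed.

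**Conclusion.** The duration analysis should change. As written, it handles ongoing responses as ended, gives no end date to those who stop without loss or never enter the LTE, and caps the two reported groups 24 weeks apart (88 to 99 against 64 to 75 weeks from first response). The cap arithmetic assumes nominal visit weeks and initial response as the start date. The 6- to 17-week difference in means rests on assumed loss rates and is illustrative only.

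For the stability proportion, the defect is a missing specification past Week 53, which can affect placebo-origin first responses at Weeks 30 to 37. The documents do not establish a general bias against the placebo-randomized group. They also do not give the number who first respond in those weeks or do not enter the LTE, so the effect cannot be sized. This is an other-secondary, descriptive endpoint outside the fixed testing sequence, and no confirmatory conclusion depends on it.

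**What to change.** In SAP Section 3.3.2.1:

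1. **Duration.** Analyze time from initial response to loss of response by Kaplan-Meier, reporting the median and quartiles with 95% CIs, as Protocol Section 10 already states for time-to-event variables. Censor at the last on-treatment platelet count. Add a sensitivity analysis counting discontinuation, or a start or increase of CS or TPO-RA, as loss.
2. **Stability proportion.** State that placebo-origin first responses at Weeks 30 to 37 use the scheduled LTE counts (Weeks 57 and 61), and that weeks with no scheduled visit are not scored as missing. Show participants without 24 observable weeks both ways: as non-responders and as not evaluable.
3. **Optional.** A summary requiring two-thirds of counts at or above 50,000/µL may be added as supplementary. It should not replace the protocol definition.

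The cost is SAP wording and a little more programming, with no new data. One limitation remains: with 28-day LTE visits, two successive low counts meet the four-week failure rule, where weekly counts need five. The report should note this beside the by-group results.

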2.5. Study Design Rationale

Study PRN1008-018 is a randomized, double-blind, parallel-group, multicenter, placebo-controlled study with a blinded treatment period of up to 24 weeks followed by an open label period of 28 weeks, and a safety follow-up period of 4 weeks, which is intended to evaluate the efficacy and safety of oral rilzabrutinib in participants with refractory or relapsed ITP of >3 months duration in participants aged 18 years and above, and of >6 months duration in pediatric participants aged 12 to <18 years (see [Appendix 10.7](#) for EU [EEA countries], where an age range of 10 to <18 years is applicable). Participants who are eligible at the end of the open label period can be considered for a long-term extension (LTE).

Placebo has been selected as the comparator to rilzabrutinib, as there are no globally approved medicinal products, other than CS (approved in EU but not United States [US]) that could serve as a suitably rapid-acting and active comparator. Use of placebo is ethical in this context, as participants who are on concomitant ITP medications (an oral CS and/or a thrombopoietin receptor agonist [TPO-RA]) will be eligible for the study. Participants have to have an inadequate response to these medications as evidenced by the average of two platelet counts below 30,000/ μ L (with no platelet count greater than 35,000/ μ L) and will have to maintain stable doses of these medications from 14 days before Study Day 1 and until the last dose of study medication. In addition, the use of rescue medications (limited to IVIg, anti-D, CS, and platelet infusion only) will be permitted to increase platelet counts or prevent bleeding when platelet counts are less than 20,000/ μ L, or for bleeding or wet purpura.

The marketed BTK inhibitor, ibrutinib, has been studied in combination with rituximab in the treatment of chronic lymphocytic leukemia without evidence of increased drug-related AEs ([Burger 2017](#)). There is no prior drug interaction potential between anti-CD20 biologic drugs and the small molecule rilzabrutinib.

The primary purpose of the 28-week, open label period is to allow access to study drug for participants who were on placebo medication as well as to evaluate durability of clinical response and accrue additional long-term data on the safety of rilzabrutinib.

The LTE is designed to further evaluate durability of clinical response and accrue additional long-term data on the safety of rilzabrutinib.

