6.6.2. Particular Permissible Medications

The following medications are permitted for use during the study:

- ITP medications, an oral CS and/or a TPO-RA (authorized for the treatment of ITP)

Note:

- These medications must be maintained at stable doses from 14 days before Study Day 1 and until the last dose of study medication. Adjustments in the doses of concomitant ITP medications will be permitted for associated safety concerns only.
- Administration of corticosteroids and TPO-RAs should follow corresponding updated package inserts/SmPCs of the marketing authorization.
- Tapering is allowed during LTE period only due to achieving durable platelet response, and would follow the following guidelines with 2 weekly platelet counts between tapers:
 - 10 mg/day every one to two weeks from an initial dose >40 mg of prednisone or equivalent per day
 - 5 mg/day every one to two weeks at prednisone doses ≤ 40 to >20 mg or equivalent per day
 - 2.5 mg/day every one to two weeks at prednisone doses ≤ 20 to >10 mg or equivalent per day
 - 1 mg/day every one to two weeks at prednisone doses ≤ 10 to >5 mg or equivalent per day
 - 0.5 mg/day every one to two weeks at prednisone doses ≤ 5 mg or equivalent per day down to zero. This can be achieved by alternating daily doses (eg, 5 mg on day one and 4 mg on day two)
 - Dose of corticosteroid can be up titrated if platelet counts fall below $50,000/\mu L$ on two consecutive measurements
- IVIg or high- dose CS, platelet infusion, or anti-D immunoglobulin infusion as rescue medications

- Clinically relevant drugs that are substrates of CYP3A, including those considered to be sensitive CYP3A substrates. Appropriate caution should be used when co-administering sensitive CYP3A substrates with rilzabrutinib, including an assessment of medical risk-benefit for each medication. Consideration should also be given to avoidance of high doses, dose reduction, or replacement of sensitive CYP3A substrate drugs
- H₂ receptor blocking drugs (ranitidine or famotidine) and antacids are permitted provided they can be given 2 hours or more after administration of rilzabrutinib or placebo

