#### *General considerations for efficacy analyses*

The statistical tests will be two-sided tests at a nominal 5% significance level for primary efficacy endpoint and key secondary efficacy endpoints.

Primary and secondary efficacy analyses will be performed in the ITT population, unless otherwise specified. The analyses of primary and key secondary endpoints are to compare the rilzabrutinib treatment group and the placebo treatment group.

The study primary and key secondary efficacy analyses will be based on the adult population at the time when the last adult participant has completed the 24-week blinded treatment period. The results based on the adults at the early analysis will be considered as final and serve as the basis

for registration application submissions. A separate analysis for the pediatric population will be similarly performed after pediatric participants have completed the blinded treatment period which may be at the same or different time when the adults have completed the blinded treatment period. The efficacy analyses on the pediatric population will be descriptive. Final analysis will be performed at the completion of the study. Additional analyses (eg, OL and LTE parts) may be performed before the final analysis. Please refer to [Section 3.8](#) for more details.

The randomization stratification factors will include splenectomy status (yes, no) and severity of thrombocytopenia (platelet counts  $<15,000/\mu\text{L}$ ,  $\geq 15,000/\mu\text{L}$ ).

For platelet count, a scheduled measurement will be used if it is available. Otherwise, an unscheduled measurement will be allocated to a scheduled visit if it is within the analysis window of the scheduled visit (see details in [Section 5.4](#)).

Rescue medications are recorded in eCRF by the investigator. Per protocol, rescue medications include IVIg, high-dose CSs, platelet infusion, and anti-D immunoglobulin infusion intended to increase platelet counts or prevent bleeding when platelet counts are less than  $20,000/\mu\text{L}$ , or for bleeding or wet purpura. Other rescue medications are not permitted.

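### In the LTE, platelet counts under a newly started or above-baseline corticosteroid or TPO-RA count as rilzabrutinib response, because the SAP discounts only rescue, missing counts and discontinuation

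*SAP*

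**What the plan says.** **Medication rules in the LTE.** Footnote a to Protocol Table 3, repeated in Protocol Section 4, permits retreatment at the baseline regimen and adds that "changing the dose or initiation of new ITP medications (an oral CS and/or a TPO-RA) will also be allowed". No platelet condition is attached to that sentence. In the tapering guidance of Section 6.6.2, "Dose of corticosteroid can be up titrated if platelet counts fall below" 50,000/µL on two consecutive measurements. The same section, like the Synopsis, also says of concomitant CS and TPO-RA: "These medications must be maintained at stable doses from 14 days before Study Day 1 and until the last dose of study medication", with adjustment for safety reasons only.

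**Analysis rules.** SAP Section 3.3.2.1 gives two discounts for stability of response. Missing counts are non-response, and "platelet counts within 4 weeks of rescue regimen will be considered as no response". SAP Section 3.1 lists what rescue is: "rescue medications include IVIg, high-dose CSs, platelet infusion, and anti-D immunoglobulin infusion". Duration of stable response runs to the first spell of consecutive counts below 50,000/µL lasting 4 weeks or longer, or to "12 months after entering LTE", whichever comes first. It is summarised descriptively in the rilzabrutinib safety population and by randomised group. Footnote a to SAP Table 2 extends that table's strategies to endpoints not listed in it, including those of the LTE. For platelet endpoints, those strategies address rescue and discontinuation of study treatment.

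**Purpose.** Protocol Section 2.5 states that "The LTE is designed to further evaluate durability of clinical response" and to collect long-term safety data.

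**The concern.** A participant whose counts are falling in the LTE may be given a TPO-RA or a higher dose of oral CS. If counts recover, the SAP keeps counting those weeks as response and keeps the duration running, although the recovery may come from the added drug. The durability figures then describe rilzabrutinib plus whatever was added, and any error is upward, in participants who needed more treatment.

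The protocol applies a different principle in the blinded period. Its primary efficacy analysis (Section 10.3.9, and Appendix 10.7 for the EEA and UK) groups an increase in the dose of allowed concomitant ITP drugs with rescue and counts it as failure. The SAP does not repeat that wording, and nothing equivalent governs the LTE, which is the period in which such changes are expressly allowed.

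**Working it through.** **Step 1. Side-by-side comparison.**

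| Event in the LTE | Permitted by protocol | SAP rule for platelet endpoints |
|---|---|---|
| IVIg, high-dose CS, platelet infusion, anti-D | Yes, as rescue | No response for 4 weeks |
| New oral CS (not high-dose rescue) or new TPO-RA | Yes (Table 3 footnote a; Section 4) | None |
| Higher dose of oral CS or TPO-RA | Yes (same places; CS also in Section 6.6.2) | None |
| Missing count | – | No response (stability) |
| Stopping study drug | – | No response afterwards (via Table 2) |

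The second and third event rows are the gap.

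**Step 2. Length of the LTE on nominal days.** SAP Table 12 puts week n at day 1 + 7 × (n − 1), so Week 53 is Day 365. With 12 visits 28 days apart, Month 12 falls on 365 + 12 × 28 = Day 701, which matches Table 12. The LTE therefore contributes 701 − 365 = 336 days.

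**Step 3. Share of the longest possible duration that falls in the LTE.** The start is taken as the first qualifying count.

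| Arm | First response | Longest duration | LTE share |
|---|---|---|---|
| Rilzabrutinib | Week 2 (Day 8) | 701 − 8 = 693 days | 336/693 = 48% |
| Rilzabrutinib | Week 13 (Day 85) | 701 − 85 = 616 days | 336/616 = 55% |
| Placebo | Week 26 (Day 176) | 701 − 176 = 525 days | 336/525 = 64% |
| Placebo | Week 37 (Day 253) | 701 − 253 = 448 days | 336/448 = 75% |

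**Step 4. The 24-week stability window.** In the rilzabrutinib arm the latest window ends at Week 13 + 24 = Week 37, before the LTE. In the placebo arm it ends between Week 26 + 24 = Week 50 and Week 37 + 24 = Week 61. Week 61 is Day 421, so the window can run 421 − 365 = 56 days (8 weeks) into the LTE. Only for these participants can added treatment enter the stable-responder proportion itself.

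**Step 5. Illustration for one participant.** Counts are assumed to stay at or above 50,000/µL to Day 701 after the addition. The SAP credits 701 − 57 = 644 days for a response starting on Day 57, and 701 − 204 = 497 days for one starting on Day 204 (Week 30, placebo arm).

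| Drug added or raised | Credited days after it | Share of 644 | Share of 497 |
|---|---|---|---|
| Day 393 (LTE Month 1) | 701 − 393 = 308 | 48% | 62% |
| Day 449 (Month 3) | 252 | 39% | 51% |
| Day 533 (Month 6) | 168 | 26% | 34% |
| Day 617 (Month 9) | 84 | 13% | 17% |

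**The case against.** **Low stakes.** The fixed testing sequence covers blinded-period endpoints only. Duration is descriptive, LTE endpoints are exploratory without testing, and there is no LTE control arm, so no treatment comparison is biased. All of this stands. It limits the weight of the point but does not remove it.

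**Added treatment is already reported.** The SAP plans percent change in CS and TPO-RA dose, LTE monotherapy, and a summary of concomitant ITP drugs. None of these changes the platelet rules. The dose change is taken only at Week 53 and after 12 months of LTE, and it has no denominator for a participant who had no such drug at baseline. The LTE proportion endpoints count only reductions or stops.

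**Up-titration belongs to the taper guidance.** Raising CS after a taper may only restore the baseline dose, which adds nothing to the regimen under which response arose. This is right, and the point covers only new drugs and doses above baseline.

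**Loss is still captured.** A reader might infer that early up-titration means loss of response is never recorded. The documents do not support that. LTE visits are 28 days apart in the first year, the SAP uses a scheduled count in preference to an unscheduled one, and a spell of low scheduled counts lasting 4 weeks still ends the duration. Participants below the LTE response threshold at two consecutive visits may also be withdrawn. These safeguards work when the added drug fails. They do nothing when it succeeds, which is the case at issue.

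**The choice of strategy is a preference.** Permanent non-response is harsher than the 4-week discount for rescue. That is fair, and it is a reason to keep the present rule alongside.

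**Conclusion.** The gap is real. Followed exactly, the SAP credits to rilzabrutinib the platelet counts obtained under a new or above-baseline CS or TPO-RA in the LTE. It reaches three outputs: the descriptive duration of stable response (at most 336 days per participant), the exploratory LTE response rates, and up to about 8 weeks of the 24-week stability window for placebo-arm participants only. The day counts use nominal visits, and the illustration assumes that response persists after the addition.

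Two larger conclusions are tempting and not supported. One is that a stated share of LTE responders is misattributed: the documents give no rate of added treatment, so no share can be computed. The other is that the LTE rescue rate falls because a TPO-RA replaces rescue: nothing in the documents shows this. The primary and key secondary tests do not change. A high-dose CS recorded as rescue is already discounted.

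Separately, the protocol's instruction to hold CS and TPO-RA doses stable to the last dose of study drug conflicts with its LTE permissions, and the passages must be reconciled.

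**What to change.** In SAP Sections 3.3.2.1 and 3.4.1:

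1. Define as an intercurrent event in the LTE any newly started CS or TPO-RA, or any dose above the participant's baseline dose. A return up to, but not above, the baseline dose is not counted as added treatment.
2. End the duration of stable response on that date, and count later LTE platelet values as no response.
3. Keep the current rule as a supplementary analysis.
4. Report the number and timing of these changes.

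In the protocol, reconcile the stable-dose text (Synopsis and Section 6.6.2) with the LTE permissions (Table 3 footnote a and Section 4).

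The cost is SAP wording and some programming. Concomitant medications are recorded at each LTE visit, the planned dose-change endpoints already presuppose dose data, and LTE efficacy is the last of the five analysis steps in SAP Table 10. The downside is somewhat lower LTE durability figures.
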